## Abbreviations

| ACT   | Artemisinin-based Combination Therapy              |
|-------|--|
| CNP   | Copy Number Polymorphism                           |
| DBS   | Dried Blood Spot                                   |
| DMR   | Department of Malaria Research                     |
| DNA   | Deoxyribonucleic acid                              |
| ERC   | Ethics Review Committee                            |
| GCP   | Good Clinical Practice                             |
| GMS   | Greater Mekong Sub-region                          |
| GWAS  | Genome-Wide Association Study                      |
| ICH   | International Conference on Harmonization          |
| ID    | Identification                                     |
| Ν     | Number (typically refers to subjects)              |
| NMCP  | National Malaria Control Program                   |
| PCR   | Polymerase Chain Reaction                          |
| PI    | Principal Investigator                             |
| PMI   | U.S. President's Malaria Initiative                |
| SOP   | Standard Operating Procedure                       |
| UMB   | University of Maryland, Baltimore                  |
| URC   | University Research Co.                            |
| USA   | United States of America                           |
| USAID | United States Agency for International Development |
| VBDC  | Vector Borne Disease Control                       |
| WHO   | World Health Organization                          |
| WWARN | Worldwide Antimalarial Resistance Network          |

## **Protocol Summary**

| Title:                  | Evaluation of the performance of a highly-sensitive rapid diagnostic
test (hsRDT) versus conventional RDT (cRDT), compared with
polymerase chain reaction (PCR) as the gold standard, in reactive case
detection of malaria infections in Rakhine State, Myanmar |
|-------------------------|--|
| Population:             | Adults and children at least 6 months of age in a specified study site   |
| Number of Sites:        | One  |
| Study Duration : | One year   |
| Subject Duration:       | One encounter lasting no more than 30 min  |

#### **Study objectives**:

**General objective**: To evaluate the performance of the highly-sensitive rapid diagnostic test (hsRDT), developed by SD Bioline, *versus* conventional RDT (cRDT), compared with PCR as the gold standard, in reactive case detection to identify additional malaria infections in Rakhine State, Myanmar

#### **Specific objectives**

1. To evaluate the prevalence of malaria identified by the new hsRDT in comparison with that by cRDT and PCR

Outcomes: test positivity rate by cRDT, hsRDT and PCR, respectively

2. To assess the diagnostic performance characteristics of hsRDT *versus* cRDT, using PCR as gold standard, in the detection of *P.falciparum* infections

Outcomes: Sensitivity, specificity, positive and negative predictive value of hsRDT and cRDT

3. To evaluate correlation of detection capability between cRDT and hsRDT

Outcomes: Correlation of test positivity rate by the three different study tests

4. To identify risk factors associated with malaria infection, including but not limited to, socio-demographic factors and travel history related with malaria index cases

Outcomes: Relative risk of malaria in association with different risk factors identified

# **3.** Background information and scientific rationale

#### **3.1. Background and introduction**

Myanmar, along with several other countries in the Grater Mekong Sub-region (GMS), is committed to eliminate malaria by 2030. In the National Plan for Malaria Elimination in Myanmar (2016–2030), the NMCP recommended that standard operating procedures (SOPs) for malaria active case detection (ACD) should be developed, and that the role of rapid diagnostic tests (RDTs), microscopy, and PCR-based techniques in ACD at different levels of the transmission-reduction and elimination phases be evaluated.

Recent epidemiological data indicates that 30-50% of all malaria infections exist in a form of asymptomatic infection (also known as "chronic malaria") where the parasite density is generally below the limit of detection of all point-of-care diagnostic tests [1]. The requirement for more sensitive diagnostic tests for malaria is predicated on the idea that malaria elimination may require eradicating all parasites from all infected persons, not just those with clinical symptoms [2]. "Asymptomatic"—or more accurately, *subclinical* malaria—has long been recognized in semi-immune Africans [3], but not in Southeast Asia where malaria transmission is generally lower. Many believed that subclinical infections are unlikely in low transmission settings, partly due to a long held dogma that partial immunity does not develop to allow for such low grade infections, and partly to the lack of detection methods adequately sensitive to identify very low parasite density typically found in the GMS [4-6].

New "ultrasensitive" PCR-based tests, with a lower limit of detection 16–22 parasites/mL [4, 7-9], have recently found unexpectedly high rates of subclinical malaria in Southeast Asia. These infections are missed by standard diagnostics such as microscopy or conventional RDT which have a lower limit of detection about 100 parasites/uL. Though the PCR is adequately sensitive to detect these low-density infections, its utility is quite severely limited by its complexity, requirement for advanced skills and infrastructure, cost, and by the fact that it is not a point-of-care test. Today's malaria elimination toolkit essentially consists of prompt diagnosis and treatment using rapid diagnostic tests (RDTs) and artemisinin-based combination treatments (ACTs), vector control methods, and surveillance using RDTs and/or microscopy. The available diagnostic tests are inadequate to detect these low-density malaria infections, and new tools are urgently needed.

Three studies, a survey, and a systematic review assessing the role, appropriateness and benefits of the ACD strategy, both proactive and reactive, in low transmission settings have been recently conducted in Cambodia, Indonesia, Thailand, India and other Asian-Pacific countries [10-12]. The data clearly indicated that the ACD strategy needs to be optimized based on the local context, and on evidence for the adoption of improved methods. The need for better, cheaper and more accurate diagnostic tools, with an increased capacity to detect low density malaria infections, was highlighted in recent literature.

To fill this critical gap, a new hsRDT that has a potential to be at least 10- to 20-fold more sensitive for detecting low density infections than standard cRDT was developed (Standard Diagnostics Bioline Inc. Gyeonggi-do, Republic of Korea), and is now under field evaluation in several malaria endemic countries. This test is similar in design to cRDT, using a handheld point-of-care laminar flow test to detect low levels of the *P. falciparum* antigen Histidine Rich Protein 2 (HRP2), which is also one of the detection targets of cRDT. Initial prototype testing of the new hsRDT designed to detect the *P. falciparum*-specific antigen *HRP2* in a format

similar to the current cRDT resulted in a limit of detection (LOD) of *HRP2* of about 80 pg/mL compared to cRDTs with a LOD of 800–1000 pg/mL (personal communication, [name], Diagnostics & Global Health, Bill & Melinda Gates Foundation).

We propose to evaluate the role of this new hsRDT in the setting of reactive case detection (RCD) in specified townships where malaria prevalence has been steadily declining. Our primary goal is to assess whether or not this new hsRDT performs significantly better than cRDT in identifying subclinical submicroscopic infection, and to subsequently evaluate if hsRDT can be used for effective ACD in Myanmar. The proposed study may shed light on the development of national standard operating procedures (SOPs) for ACD as recommended by the NMCP. The development of these SOPs are ongoing, and our study may provide timely and relevant contribution for their development, particularly assessing the detection accuracy and utility of the new hsRDTs when used as a screening tool in the RCD strategy. Additional useful information can be obtained on the applicability, cost, and operational challenges faced during the field implementation.

The proposed study also addresses PMI elimination or priority to "Evaluate the utility and scalability of more sensitive diagnostic tools (e.g. highly-sensitive RDTs, PCR, etc.) in an elimination context, including their utility for reactive or proactive case detection." It will also contribute to current PMI research activities comparing RCD with RDTs to focal Mass Drug Administration (MDA) planned for Madagascar and Ethiopia. The Madagascar study will also include the hsRDT in their RCD arm. If the test of this hsRDT in detecting additional malaria infections around index cases shows good field performance, further trials can be planned in Myanmar to evaluate its role in malaria elimination.

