# 5. Methodology

# 5.1. Study Design & Overview

This is a prospective community-based single-center reactive case detection (RCD) study to assess the performance of hsRDT versus cRDT in identifying individuals with malaria infection ("Secondary case") in a population living and/or working in a close physical proximity to an "index case."

"Index case" is defined as a malaria infection identified by passive surveillance by local health services (rural health center, sub-centers) or village malaria workers (VMWs), by cRDT or microscopy.

"Secondary case" is defined as any malaria infection identified by any of the study diagnostic test: cRDT, hsRDT or PCR, regardless of the presence of acute clinical illness. The secondary cases will be identified actively and systematically around the residence, or work place if relevant, of the index case.

The study will be initiated after obtaining administrative (Myanmar MoHS, NMCP, PMI) and ethical approval (Myanmar DMR ERC, CDC IRB and UMB IRB) from all relevant institutions. Consent, and assent and adult permission when appropriate, will be sought for all index cases and secondary cases. Only those who are eligible and provide informed consent will be enrolled in the study.

All index cases parasitologically confirmed by cRDT or microscopy will be appropriately and promptly notified to the study team, using mobile phone technology where possible, to ensure timely enrollment. The home of the index case, or work place when relevant, will be visited within three days of the diagnosis, and s/he will be interviewed with a standardized case investigation form. During the visit, all members of the index case household and all members of the nearest 10 households, aged 5 years or above, will be invited to participate in the study. All participants in the study will be interviewed with a structured questionnaire, tested with cRDT and hsRDT, and a dried blood spot (DBS) will be collected for subsequent PCR analysis. All cases parasitologically confirmed by cRDT or hsRDT will be appropriately treated, following the national treatment guideline. DBS samples will be collected, processed and stored until analysis following the World Wide Antimalarial Resistance (WWARN) Molecular Testing for Malaria Standard Operating Procedures DBS Sample Collection and Transportation (http://www.wwarn.org/learning/procedures/dbs-sample-collection-andtransportation).

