The prevalence of secondary malaria cases (number positive /number tested), by cRDT and hsRDT will be compared, using PCR as gold standard. Using simple analysis of performance characteristics, the sensitivity and specificity of hsRDT will be estimated in the study population. Potential correlation between the detection rate by cRDT, hsRDT and PCR will be assessed.

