## 6.2. PCR assay from dried blood spot

DNA will be extracted dried blood spots using a validated new extraction method developed by our group (Zainabadi et al. "A dried blood spot based ultrasensitive detection method for asymptomatic malaria" Oral presentation at the 57the annual meeting of American Society of Tropical medicine and Hygiene, November 2016). As much of the molecular analyses as possible will be done at the Advanced Molecular Research Center of the Department of Medical Research, under the Myanmar Ministry of Health. Extracted DNA will be subjected to ultra-sensitive qPCR using well-established techniques that currently have a lower limit of detection of 22 parasites/mL (9). PCR will be done in Myanmar with some duplicate samples analyzed at the University of Maryland for quality control purposes.

Future studies of parasite DNA derived from samples may be conducted without restriction. *No other studies on any topics beyond what is described in this protocol and consent/assent forms or on human DNA will be done unless specific permission for additional studies is obtained from the relevant IRBs.* Study participants will have the right to withdraw their permission for further use of their samples at any time during and after the study.

Samples will be batched and shipped periodically to the DMR laboratory and/or the laboratories at the University of Maryland in Baltimore or CDC-Atlanta. DBS specimens will be shipped at room temperature and desiccant will be replaced upon receipt. Specimen receipt will be logged using a system designed at UMB using the Freezer works program. The laboratory contact at DMR is [name] [name], E-mail: [contact]. The laboratory contact at UMB is the lab supervisor [name] E-mail: [contact].

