# 7. Statistical consideration and Data Management

## 7.1. Power calculation with available sample size

The primary limitation is the size of population that needs to be screened since malaria burden may be low in the study sites, and associated financial costs and logistical difficulties.

The primary endpoint of this proposed study is the prevalence of secondary malaria cases identified by hsRDT in comparison with usPCR prevalence. Based on our current data on prevalence of *P. falcipaum* in 2016, and logistical and financial considerations, the recruitment of 50 index cases is feasible in a given study period. This will give us a total of 1980 individuals for testing of secondary cases in ACD, assuming the average household member of 4.5, 11 households for each index case (counting the household of the index case) and a refusal rate of 20% (4.5 persons/HH x 11 HH x 50 index cases x 0.80=1980).

We conservatively estimate that hsRDT will detect 20% of usPCR+ *P. falciparum* infections (i.e., sensitivity of hsRDT=0.2 using usPCR as gold standard). We expect very few recently treated individuals to be enrolled in the study, so that hsRDT should only rarely give a positive result when usPCR does not. Hence we assume that the specificity of hsRDT is 0.995. Table 1 shows estimated statistical power that can be achieved with the proposed sample size of 1980 for comparing the prevalence by hsRDT and the prevalence by usPCR, at different malaria prevalence by usPCR and different sensitivity of hsRDT, using a two-sided McNemar test with a Type I error of 5%. (PASS version 11. NCSS, LLC. Kaysville, Utah, USA)

As shown in Table 1, if the sensitivity of hsRDT is 0.2 and the specificity of hsRDT is 0.995, a sample size of 1980 subjects achieves at least 92% power to detect the difference in prevalence between hsRDT and usPCR when the malaria prevalence is 2% or higher. If the sensitivity of hsRDT is 0.5 (see the last four columns of Table 1), a sample size of 1980 subjects achieves at least 86% power when the malaria prevalence is 3% or higher. If the prevalence of malaria is higher, the performance of hsRDT will be better with a higher sensitivity and positive predictive value.

 Table 1. Statistical power expected with proposed sample size of 1980 at different malaria

| prevalence and different sensitivity of hsRDT (assumed sensitivity of 20% or 50% and |
|--|
| specificity 99.5%)   |

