# 7.2. Analytical Plan

All data will be double-entered into Epi-Info and any discrepancies will be reviewed against the paper forms. All analyses will be conducted using Stata/SE (version 14), using data from the participant interviews and the three parasitological tests.

The malaria test positivity rate will be calculated as a proportion of samples tested that are positive using cRDT, hsRDT and PCR, respectively. Corresponding 95% confidence intervals (CIs) will be computed using exact method. A 2x2 table method will be used to calculate the sensitivity, specificity, positive and negative predictive values of hsRDT (and cRDT) and their corresponding 95% CIs using PCR as gold standard. The malaria prevalence by each test (e.g., the rate of malaria test positive) will be compared between each two tests (hsRDT vs PCR; cRDT vs PCR; hsRDT vs cRDT) using McNemar test. All statistical tests will be performed with a two-sided significance level of 0.05.

Descriptive analysis will be conducted to assess socio-demographics characteristics. Univariate analysis will include t-test and non-parametric methods for continuous variables and chi-square test for comparison of categorical variables. Multi-level regression models will be developed to examine risk factors significantly associated with malaria infections, accounting for clustering by index case.

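### The primary goal concerns subclinical submicroscopic infection, but no planned analysis isolates that group or confines the hsRDT-versus-cRDT comparison to PCR-confirmed infections

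*Combined protocol and SAP*

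**What the plan says.** Section 3.1 states the aim as a comparison of the two RDTs in a specific kind of infection: "Our primary goal is to assess whether or not this new hsRDT performs significantly better than cRDT in identifying subclinical submicroscopic infection". The same section gives a density that bears on the word submicroscopic, since it refers to "standard diagnostics such as microscopy or conventional RDT which have a lower limit of detection about 100 parasites/uL".

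The rest of the plan is not specific to density or symptoms:

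- Section 7.1: "The primary endpoint of this proposed study is the prevalence of secondary malaria cases identified by hsRDT in comparison with usPCR prevalence".
- Section 5.1, on accuracy: "Using simple analysis of performance characteristics, the sensitivity and specificity of hsRDT will be estimated in the study population".
- Section 7.2, on accuracy: "A 2x2 table method will be used to calculate the sensitivity, specificity, positive and negative predictive values of hsRDT (and cRDT"; PCR is the reference and 95% confidence intervals are given. No stratum is named.
- Section 7.2 also plans McNemar tests of test positivity for each pair of tests, including hsRDT against cRDT.
- Section 5.1 counts secondary cases "regardless of the presence of acute clinical illness".
- Specific objective 2 limits the accuracy question to *P. falciparum*, which restricts species but not density.

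Contacts are "tested with cRDT and hsRDT, and a dried blood spot (DBS) will be collected for subsequent PCR analysis". Microscopy is not among the tests listed for them; Section 3.3.1 mentions a blood smear only when describing finger-stick risks. The reference assay could supply a density, because in Section 6.2 "Extracted DNA will be subjected to ultra-sensitive qPCR using well-established techniques".

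**The concern.** The new test is claimed to be better at low density, and that is where Section 3.1 places the question. Section 3.1 puts the limit of standard tests at about 100 parasites/µL, and Section 6.2 puts the PCR limit at 22 parasites/mL. The ratio is 100,000 / 22, or about 4,500-fold. A pooled set of PCR-positives can therefore mix infections that both RDTs should find with infections that only hsRDT might find, in proportions that depend on who is found around index cases.

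Two gaps follow. The pooled sensitivity of hsRDT does not reveal its sensitivity at low density. And the one planned hypothesis test of hsRDT against cRDT counts every discordant pair, whether or not PCR confirms an infection. The results are meant to inform national procedures for active case detection, so it matters whether an apparent hsRDT advantage consists of extra low-density infections or of PCR-negative positives.

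**Working it through.** **Inputs.** From Section 7.1 and Table 1: N = 1980, PCR prevalence 2%, hsRDT sensitivity 0.20, specificity 0.995, two-sided McNemar test at 5%. From Section 3.1: about 100 parasites/µL. The documents give no density distribution for contacts and no planning values for cRDT, so every split below is an assumption.

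**1. The plan's own figures.** N = 4.5 × 11 × 50 × 0.80 = 1980, as stated. Positivity by hsRDT = 0.02 × 0.20 + 0.98 × 0.005 = 0.0040 + 0.0049 = 0.0089, shown as 0.009 in Table 1. With discordant probabilities 0.02 × 0.80 = 0.016 and 0.0049, exact McNemar power is 0.923, against 0.92 stated. The planning case reproduces, but it concerns hsRDT against PCR. No power is given for hsRDT against cRDT.

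**2. What the hsRDT positives consist of.**
- PCR-positives: 1980 × 0.02 = 39.6, about 40.
- True detections: 39.6 × 0.20 = 7.9, about 8.
- False positives: 1980 × 0.98 × 0.005 = 9.7, about 10.

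False positives are 9.7 / (9.7 + 7.9) = 55% of expected hsRDT positives.

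**3. Effect on the hsRDT-versus-cRDT McNemar test.** Suppose hsRDT found no infection that cRDT missed, and cRDT had no false positives (assumption). The discordant pairs would be about 10 against 0, and the exact two-sided p is 2 × 0.5^10 = 0.002. The test would be significant with no additional infection found. If cRDT had the same false-positive rate, the two sets would balance in expectation. The plan does not settle which applies.

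**4. Low-density sensitivity behind a pooled 20%.** Let h be the share of PCR-positives at or above 100 parasites/µL. Then pooled S = h × Se_high + (1 − h) × Se_low. Take Se_high = 1 and about 40 PCR-positives with 8 detected:

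| High-density and detected (assumed) | h | Se_low |
|---|---|---|
| 2 of 40 | 0.05 | (8 − 2)/(40 − 2) = 16% |
| 4 of 40 | 0.10 | (8 − 4)/(40 − 4) = 11% |
| 8 of 40 | 0.20 | (8 − 8)/(40 − 8) = 0% |

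**5. What a stratified analysis would rest on.** Assume that 30–80% of PCR-positives are submicroscopic. At 2% prevalence the stratum holds 39.6 × 0.30 = 12 to 39.6 × 0.80 = 32 infections. With none detected, the exact upper 95% limit is 1 − 0.025^(1/n): 26% for n = 12 and 11% for n = 32. At 12% prevalence there are 237.6 PCR-positives, so 71 to 190 in the stratum.

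**6. What a paired test among PCR-positives can show.** Take the 4-of-40 row, with cRDT finding those 4 and nothing else. The sensitivities are 8/40 = 20% and 4/40 = 10%, the discordant pairs are 4 against 0, and p = 2 × 0.5^4 = 0.125. Six one-directional pairs are needed for p = 2 × 0.5^6 = 0.031. At 6% prevalence and the same proportions, 118.8 × 0.10 = 11.9 discordant pairs would be expected.

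**The case against.** The strongest reply is that the goal is comparative and the plan already reports both sensitivities in the same people. If all 8 detected infections were high-density, cRDT should find about the same 8. The plan would then report about 20% for each test, correctly showing no advantage. Infections found by both tests largely cancel, and a PCR-positive infection found by hsRDT but missed by cRDT is probably below about 100 parasites/µL. This stands, so a reader who infers that the plan cannot address its own question goes too far. What remains is that Section 7.2 neither tabulates nor tests that cell, and the McNemar test it does plan includes PCR-negatives.

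A reader might also infer that a reported sensitivity would come entirely from high-density infections. The documents do not support that. It needs a high-density share at least equal to the pooled sensitivity, and no such share is given for contacts. The general statement in Section 3.1 that 30–50% of infections are asymptomatic does not describe this cohort.

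Third, the goal statement sits in the background text. The formal objectives and the endpoint in Section 7.1 concern all infections, and sensitivity over all infected contacts is a legitimate quantity for a screening tool. That stands, and it argues against making the low-density analysis primary, as does p = 0.125 in step 6.

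Last, 100 parasites/µL is close to cRDT's own detection limit, so a comparison confined to lower densities favours hsRDT by construction. This also stands. It is why sensitivity should be shown on both sides of the cut-off and the paired comparison made over all PCR-positives.

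**Conclusion.** The point holds as a gap between the stated goal and the planned analysis. No analysis isolates submicroscopic or subclinical infection, and the only planned test of hsRDT against cRDT is not confined to PCR-positives. At 2% prevalence and the plan's sensitivity and specificity, that test carries about 10 expected hsRDT false positives beside about 8 true detections; whether they distort it depends on cRDT's unstated false-positive rate. The pooled sensitivities give indirect evidence on the comparison. They leave hsRDT's absolute low-density sensitivity open, at 11% down to 0% for a pooled 20% if 4 to 8 of 40 PCR-positives are high-density and detected.

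This calls for a pre-specified addition. It does not show that the pooled analysis is wrong or that the primary endpoint must be replaced.

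**What to change.** In Section 7.2, keep the pooled analysis and the stated primary endpoint, and pre-specify as additional analyses:

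- a paired hsRDT-versus-cRDT comparison of sensitivity (McNemar or exact) among PCR-positive *P. falciparum* contacts, with the discordant counts shown. Index cases should be left out, since Section 5.5 enrols them because they are cRDT-positive;
- the sensitivity of each RDT, with exact 95% intervals, by qPCR density band, including below and at or above about 100 parasites/µL. State that this cut-off is the working definition of submicroscopic, because microscopy is not listed for contacts, and that it lies close to cRDT's own detection limit.

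Report by symptom status only if symptoms are recorded at the visit. The interview items listed in Sections 5.5 and 7.3 do not show this, and the annex forms were not available to check.

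No new samples or visits are needed, provided that a quantified qPCR result is kept for each sample. Section 6.2 names a quantitative assay and Section 9.2 mentions linked parasite counts, but neither commits to a density per specimen, so the plan should say so. The main cost is imprecision: with perhaps 12 to 32 low-density infections at 2% prevalence, the stratum should be presented mainly as estimation with wide intervals. The cut-off and bands should be fixed before results are seen.
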